6.1 Study treatment

Study treatment includes the investigational drugs dabrafenib (DRB436) using 50 mg and 75 mg capsules and trametinib (TMT212) using 2 mg and 0.5 mg tablets. Study treatment will be provided as global clinical open-labeled supply or commercially sourced supply. Global supplies will be packed and labeled under the responsibility of Novartis Global Clinical Supply (GCS).

6.1.1 Investigational and control drugs

Table 6-1 Investigational drug

Investigational Drug (Name and Strength)	Pharmaceutical Dosage form	Route of Administration	Supply Type	Sponsor (global or local)
DRB436 75 mg	Capsule	Oral use	Open label participant packs; bottle	Sponsor (global or local)
DRB436 50 mg	Capsule	Oral use	Open label participant packs; bottle	Sponsor (global or local)
TMT212 2 mg	Tablet	Oral use	Open label participant packs; bottles	Sponsor (global or local)
TMT212 0.5 mg	Tablet	Oral use	Open label participant packs; bottles	Sponsor (global or local)

Dispense a 3 week supply of the study treatment with instructions. Allow for +/- 7 day visit window. Record dose reductions, dose interruptions/delays, and/or dose escalations in CRF.

6.1.2 Additional study treatments

No other treatment beyond investigational drug and control drug are included in this trial.

6.1.3 Treatment arms/group

This is a single arm study. Participants meeting all eligibility criteria as defined in [Section 5](#) will receive dabrafenib 150 mg BID in combination with trametinib 2 mg once daily, starting from Day 1.

6.1.4 Treatment duration

Study treatment will be administered until the participant experiences one of the following: disease progression by RECIST 1.1 as determined by investigator assessment (and not meeting the criteria in [Section 6.1.4.1](#)), unacceptable toxicity, pregnancy, treatment discontinuation at

the discretion of the investigator or the participant, start of a new anti-neoplastic therapy, withdrawal of consent, lost to follow-up, death, or study termination by the sponsor.

6.1.4.1 Treatment beyond disease progression

Participants will be permitted to continue study treatment beyond disease progression per RECIST 1.1 as assessed by investigator review provided they meet all the following criteria:

1. Informed consent for treatment beyond disease progression is provided by the participant
2. The participant experienced a confirmed tumor response according to RECIST 1.1 while receiving study treatment or disease under study has remained no worse than stable for a period of at least 3 months while receiving study treatment.
3. Absence of signs and symptoms of clinical disease progression despite disease progression based on RECIST 1.1 criteria.
4. No treatment-related AEs of CTCAE grade 4 or serious AEs (SAEs) have occurred during the last 4 weeks of study treatment
5. Participant remains with stable performance status.
6. Continuation of treatment beyond progression should not delay critical interventions to treat/prevent severe complications of disease progression (e.g. CNS metastases), or prevent participants from receiving adequate care.

Participants who meet the above criteria are permitted to continue study treatment and continue all study procedures as outlined in [Table 8-1](#). The reasons for the participant continuing treatment beyond progression will be documented in the eCRF.

In case of clinical deterioration or suspicion of disease progression, a follow-up imaging assessment should be performed promptly rather than waiting for the next scheduled assessment. Participants with evidence of further disease progression on an imaging assessment or who are no longer deriving clinical benefit will be permanently discontinued.

6.2 Other treatment(s)

6.2.1 Concomitant therapy

The investigator must instruct the participant to notify the study site of any new medication(s) he/she takes after start of study participation.

Prior antineoplastic therapies including medications, radiotherapy, and surgery are to be recorded on the separate prior antineoplastic therapy Case Report Forms during screening.

All medications, procedures, and significant non-drug therapies (including physical therapy, herbal/natural medications and blood transfusions) administered after the participant was enrolled into the study must be recorded on the appropriate Case Report Forms. Medication entries must be specific to trade name, dose and units, frequency and route of administration, start and discontinuation dates, and reason for therapy. For medications administered one time, the frequency column may reflect “once.”

Each concomitant drug must be individually assessed against all exclusion criteria/prohibited medication. If in doubt, the investigator should contact the Novartis medical monitor before

allowing a new medication to be started. If the participant is already enrolled, contact Novartis to determine if the participant should continue participation in the study.

In general, concomitant medications and therapies deemed necessary for the supportive care (e.g., such as anti-emetics, anti-diarrhea) and safety of the participant are allowed except those prohibited in [Section 6.2.2](#). Participants are permitted to use the following medications during study treatment:

- Limited-field palliative radiotherapy to non-target lesion(s) may be allowed after documented discussion with Novartis study physician as concomitant therapy such as local therapies administered during the study treatment. Any radiotherapy must be listed on the appropriate eCRF. In case of palliative radiotherapy, the participant should interrupt dabrafenib and trametinib for fractionated radiotherapy and stereotactic radiosurgery before and after radiotherapy as outlined below ([Anker et al 2016](#)).
 - Interrupt dabrafenib and trametinib \geq 3 days before and after fractionated radiation
 - Interrupt dabrafenib and trametinib \geq 1 day before and after stereotactic radiosurgery (SRS)
- Antivirus medications to manage HBV or HCV infection and/or prevent reactivation (e.g., tenofovir); supportive care.
- Medications to prevent or treat nausea or vomiting.
- Anti-diarrheal medications (e.g., loperamide) for participants who develop diarrhea.
- Pain medication to allow the participant to be as comfortable as possible.
- Bone targeted therapies (e.g., bisphosphonates, denosumab) to treat bone metastases or to prevent skeletal related events.
- Nutritional support or appetite stimulants (e.g., megestrol).
- Oxygen therapy and blood products or transfusions.
- The participant must be told to notify the investigational site about any new medications he/she takes after the start of the study drug

All medications (other than study drug) and significant non-drug therapies (including physical therapy, herbal/natural medications and blood transfusions) administered after the participant signed consent and through 30 days after the last dose of study treatment must be listed on the Concomitant Medications or the Procedures and Surgical and Medical Procedures eCRF.

Any anti-neoplastic therapy (including surgery, radiotherapy, medications) administered in the Follow-up Period after discontinuation of study treatment must be listed on Antineoplastic Medication Since Discontinuation eCRF pages including best response to therapy, if available.

6.2.1.1 Permitted concomitant therapy requiring caution and/or action

Dabrafenib

Effect of other drugs on dabrafenib

Based on in vitro studies, dabrafenib was shown to be primarily metabolized by CYP2C8 and CYP3A4. Medicinal products that are strong inhibitors or inducers of CYP2C8 or CYP3A4 are likely to increase or decrease, respectively, dabrafenib concentrations. Alternative agents should be considered during administration with dabrafenib when possible. Use caution if

strong inhibitors (e.g ketoconazole, nefazodone, clarithromycin, ritonavir, gemfibrozil) or inducers (e.g rifampin, phenytoin, carbamazepine, phenobarbital, St John's wort) of CYP2C8 or CYP3A4 are co-administered with dabrafenib.

Effect of dabrafenib on other drugs

Dabrafenib induces CYP3A4 and CYP2C9 mediated metabolism and may induce other enzymes including CYP2B6, CYP2C8, CYP2C19 and UDP glucuronosyltransferases (UGT). Dabrafenib may also induce transporters (e.g P-glycoprotein [P-gp]). Co-administration of dabrafenib and medicinal products which are affected by the induction of CYP3A4 or CYP2C9 such as hormonal contraceptives, warfarin or dexamethasone may result in decreased concentrations and loss of efficacy. If co-administration of these medications is necessary, monitor participants for loss of efficacy or consider substitutions of these medicinal products. Use caution if co-administration of CYP2C or CYP3A4 substrates with narrow therapeutic index is required. Refer to the Tafinlar label for further information.

Trametinib

Based on in vitro and in vivo data, trametinib is unlikely to significantly affect the pharmacokinetics of other medicinal products via interactions with CYP enzymes or transporters.

Dabrafenib and trametinib

Based on the mechanism of action of dabrafenib and trametinib, vaccines are not expected to have an interaction with these drugs, therefore are not prohibited. However, investigators should use their best clinical judgment on the use of live vaccines considering the potential immunocompromised state of cancer patients.

6.2.2 Prohibited medication

The following medications or non-drug therapies are also prohibited while on treatment in this study:

- Other anti-cancer therapies
- Other investigational drugs

Although not contraindicated/prohibited, certain medications drugs should be used with caution due to potential drug-drug interactions (see [Section 6.2.1.1](#)).

6.3 Participant numbering, treatment assignment, randomization

6.3.1 Participant numbering

Each participant is identified in the study by a Subject Number (Subject No.), that is assigned when the participant is first enrolled for screening and is retained as the primary identifier for the participant throughout his/her entire participation in the trial. The Subject No. consists of the Center Number (Center No.) (as assigned by Novartis to the investigative site) with a sequential participant number suffixed to it, so that each participant is numbered uniquely across the entire database. Upon signing the informed consent form, the participant is assigned to the next sequential Subject No. available.

6.3.2 Treatment assignment, randomization

Not applicable.

6.4 Treatment blinding

Treatment will be open to participants, investigator staff, persons performing the assessments, and the CTT.

6.5 Dose escalation and dose modification

6.5.1 Dose modifications

General guidelines regarding management and dose reduction for adverse events that are considered by the investigator to be related to study treatment and for which specific guidelines do not apply are provided in [Table 6-2](#). These guidelines are intended primarily for toxicities not easily managed with routine supportive care. For example, alopecia is not an indication for dose modification, nor is grade 2 nausea and vomiting that can be easily managed with anti-emetics.

The following section(s) address the specific instructions for mandatory dose modifications and recommended management for AEs considered suspected to be related to study treatment. For participants who do not tolerate the protocol-specified dosing schedule, dose interruptions or modifications are mandated in order to allow participants to continue study treatment.

If treatment related toxicities occur when dabrafenib and trametinib are used in combination, then both treatments should be simultaneously dose reduced, interrupted or discontinued with the exceptions shown below:

Exception where dose modification is necessary for only dabrafenib:

- Uveitis ([Table 6-14](#))

Exception where dose modifications are necessary for only trametinib:

- Retinal vein occlusions (RVO) ([Table 6-14](#)) and retinal pigment epithelial detachment (RPED) ([Table 6-15](#))
- Left ventricular ejection fraction (LVEF) reduction ([Table 6-13](#))
- Pneumonitis and ILD ([Table 6-10](#))

Table 6-2 Dose Modification Guidelines - General

Grade	Recommended adverse event management guidelines	Mandatory dose modification requirements
Grade 1 or Grade 2 tolerable	
• Monitor closely• Provide supportive care according to institutional standards	
• Continue dabrafenib and trametinib at the same dose level.
Grade 2 (intolerable) or Grade 3	
• Monitor closely.• Provide supportive care according to institutional standards	
• Interrupt dabrafenib and trametinib• When toxicity resolves to ≤ Grade 1 or baseline, restart dabrafenib and trametinib

Grade	Recommended adverse event management guidelines	Mandatory dose modification requirements
		
reduced by one dose level per Table 6-3.
 
 • If the Grade 2 (intolerable) or Grade 3 toxicity recurs, interrupt dabrafenib and trametinib. • If following an interruption of dabrafenib and trametinib, the AE doesn't recover to \leq Grade 1 or baseline within 3 weeks, dabrafenib and trametinib must be discontinued • Re-escalation of the participant's dose is recommended if criteria in Section 6.5.1.2 are met.
Grade 4	
 • Monitor closely. • Provide supportive care according to institutional standards 	
 • Interrupt study treatment until $=<$ Grade 1 and restart at next lower dose level or permanently discontinue study treatment • If the Grade 4 toxicity recurs, permanently discontinue study treatment

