6.5.1.1 Dose Reduction

Deviations to mandatory dose interruptions and/or reductions are not allowed. A maximum of two trametinib dose level reductions and three dose level reduction for dabrafenib are allowed. Steps for dose modifications for trametinib and dabrafenib are listed in [Table 6-3](#).

Table 6-3 Dose Modification steps for dabrafenib and trametinib

	Dabrafenib	Trametinib
Starting dose^a	150 mg BID	2 mg once daily
1st level dose reduction	100 mg BID	1.5 mg once daily
2nd level dose reduction	75 mg BID	1 mg once daily
3rd level dose reduction	50 mg BID	Not allowed

^a Dose modification should be based on the worst toxicity demonstrated at the last dose

A dose reduction below 50 mg BID for dabrafenib or below 1 mg QD for trametinib is not allowed. If a dose reduction below 50 mg BID for dabrafenib is required, dabrafenib will be permanently discontinued but these participants will be allowed to continue trametinib. If a dose reduction below 1.0 mg QD for trametinib is required, then trametinib will be permanently discontinued, but these participants will be allowed to continue dabrafenib.

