6.5.1.3 Dose Delay

For dabrafenib and/or trametinib related adverse events: if following an interruption of dabrafenib and trametinib, an AE doesn't recover to \leq Grade 1 or baseline within 4 weeks, dabrafenib and trametinib must be discontinued.

Approval from the Medical Lead is required to restart study treatment after 4 weeks.

[Table 6-4](#) provides a list of AEs of special interest and relevant sections where detailed dose modification and management requirements for relevant AEs can be found. All AEs are to be graded according to NCI-CTCAE v4.03, unless otherwise specified. Investigators should refer to the current dabrafenib and trametinib local prescribing information and/or Investigator's Brochure for additional information regarding the background of each drug and the management of other AEs or potential safety-related issues not specifically mentioned in this protocol.

Table 6-4 Reference of AEs and toxicity management guidelines

Adverse Events	dabrafenib	trametinib	Guideline
General	X	X	X
Pyrexia	X	X	X
Rash	X	X	X
Serious skin reactions	X	X	X
Hand foot skin reactions	X	X	X
Diarrhea	X	X	X
Pneumonitis / ILD		X	X
Renal function alterations	X	X	X
Hypertension	X	X	X
LVEF decrease	X	X	X
Visual changes	X (Uveitis)	X (RVO)	X
RPED		X	X
Hyperglycemia	X		X
Hemorrhage	X	X	X
Thromboembolic events		X	X
New malignancies	X	X	X
Abnormal liver enzyme tests	X	X	X

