9.1 Discontinuation

9.1.1 Discontinuation of study treatment

Discontinuation of study treatment for a participant occurs when study treatment is stopped earlier than the protocol planned duration and can be initiated by either the participant or the investigator.

The investigator must discontinue study treatment for a given participant if, he/she believes that continuation would negatively impact the participant's well-being.

Study treatment must be discontinued under the following circumstances:

- Disease progression
- Adverse events, abnormal laboratory values, or abnormal test result that indicate a safety risk to the participant as described in [Section 6.5.2](#).
- Participant/guardian decision
- Pregnancy
- Use of prohibited treatment as per recommendations in [Section 6.2.2](#)
- Any situation in which study participation might result in a safety risk to the participant

[figure not shown]
If a participant discontinues study treatment at a scheduled visit, the assessments performed at that visit can be used to fulfil the treatment discontinuation visit requirements. Laboratory assessments and other required assessments do not need to be repeated at the discontinuation visit if they were performed within 14 and 30 days, respectively, of the discontinuation visit. If the last efficacy assessment was >6 weeks prior to study withdrawal and disease progression had not been documented, efficacy assessment should be obtained.

Participants who discontinue study treatment or who decide they do not wish to participate in the study further should NOT be considered withdrawn from the study UNLESS they withdraw their consent (see [Section 9.1.2](#)). **Where possible, they should return for the assessments indicated** in the Assessment Schedule. If they fail to return for these assessments for unknown reasons, every effort (e.g. telephone, e-mail, letter) should be made to contact the participant/pre-designated contact as specified in [Section 9.1.3](#). This contact should preferably be done according to the study visit schedule.

If the participant cannot or is unwilling to attend any visit(s), the site staff should maintain regular telephone contact with the participant, or with a person pre-designated by the participant. This telephone contact should preferably be done according to the study visit schedule.

The investigator must also contact the IRT to register the participant's discontinuation from study treatment.

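### For the same unresolved Grade 2 (intolerable) or Grade 3 toxicity, Table 6-2 requires stopping both drugs after 3 weeks and Section 6.5.1.3 after 4, with no stated precedence

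*Protocol*

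**What the plan says.** Protocol Section 6.5.1 presents Table 6-2 as general guidance for treatment-related adverse events (AEs) "for which specific guidelines do not apply are provided in" that table. In its Grade 2 (intolerable) or Grade 3 row, under the mandatory requirements, both drugs are interrupted. The limit for an event that does not recover reads "Grade 1 or baseline within 3 weeks, dabrafenib and trametinib must be discontinued".

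Section 6.5.1.3 (Dose Delay) begins "For dabrafenib and/or trametinib related adverse events: if following an interruption of dabrafenib and trametinib", and its limit reads "Grade 1 or baseline within 4 weeks, dabrafenib and trametinib must be discontinued". The next sentence is "Approval from the Medical Lead is required to restart study treatment after 4 weeks".

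Three other places bear on the question:

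- The Grade 4 row of Table 6-2 says to interrupt and then "restart at next lower dose level or permanently discontinue study treatment". It has no time limit and is outside the conflict.
- Section 6.5.1.1 says "Deviations to mandatory dose interruptions and/or reductions are not allowed". It does not mention discontinuation.
- Section 9.1.1 lists among the reasons to stop treatment "Adverse events, abnormal laboratory values, or abnormal test result that indicate a safety risk to the participant as described in" Section 6.5.2. It does not refer to Section 6.5.1.

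**The concern.** Both sentences are mandatory, concern both drugs, start from an interruption and use the same recovery target. Only the number of weeks differs. Section 6.5.1.3 is not limited by grade or type of AE, so a Grade 3 related AE without its own guideline falls under both.

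What is at stake is permanent discontinuation, because the protocol glossary defines discontinuation of study treatment as stopping for good. Two sites could each rely on a current passage, and one participant would be taken off treatment while another with the same course restarts. SAP Sections 2.3.1 and 2.4.1 plan summaries of treatment discontinuations, interruptions and their reasons. Those counts could then depend partly on which passage a site had read.

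**Working it through.** No design figure is involved, so the check is a comparison of texts with a little arithmetic.

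**Scope.** Table 6-2 covers related AEs without a specific guideline, here Grade 2 (intolerable) or Grade 3. Section 6.5.1.3 covers all related AEs. The overlap is the whole of that Table 6-2 row.

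**Window.** I count days from the start of the interruption, which is an assumption because neither passage defines the start of the clock. Table 6-2 gives 3 × 7 = 21 days and Section 6.5.1.3 gives 4 × 7 = 28 days. The difference is 28 − 21 = 7 days.

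| Recovery to Grade 1 or less, or baseline | Table 6-2 | Section 6.5.1.3 |
|---|---|---|
| By day 21 | stopping not required | stopping not required |
| Days 22 to 28 | both drugs must stop | stopping not required |
| Not by day 28 | both drugs must stop | both drugs must stop; Medical Lead sentence follows |

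**Search for a ranking rule.**

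- The introduction to Section 6.5.1 separates AE-specific from general guidance. Table 6-2 and Section 6.5.1.3 are both general, so this does not rank them.
- Sections 6.5.1.1 and 9.1.1 do not settle it, as quoted above.
- The amendment summaries describe neither limit as superseded.
- The 4-week limits for pneumonitis and LVEF, and the 3-week limits for retinal pigment epithelial detachment and venous thromboembolism, belong to AE-specific guidance.

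**Creatinine (separate point).** The Section 6.5.2.7 text speaks of interruption above 2 mg/dL, or more than 0.5 mg/dL above baseline. The Grade 1 row of Table 6-11 requires interruption for a confirmed rise of more than 0.3 mg/dL, or 1.5 to 2.0 times baseline (reading the table's figure as a multiple of baseline). Take a hypothetical baseline of 0.80 and a confirmed value of 1.25 mg/dL:

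- Rise: 1.25 − 0.80 = 0.45 mg/dL, which is above 0.3 but not above 0.5.
- Ratio: 1.25 / 0.80 = 1.56, which is within 1.5 to 2.0.
- Level: 1.25 is not above 2 mg/dL.

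The table requires interruption and neither trigger in the text is met. This holds whether the table's two criteria are joined by *and* or by *or*. The text also cites Section 6.2, which covers other treatments, where Table 6-11 is evidently meant.

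**The case against.** A reader might infer that the two passages give opposite instructions, so that no site could satisfy both. The documents do not support that. Section 6.5.1.3 says when treatment must stop. It neither requires nor expressly permits treatment to continue until week 4. Stopping at 3 weeks breaches neither sentence, while restarting on day 25 after recovery in that window breaches Table 6-2. This is a remark about logic and not about which limit is clinically right.

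Nor would reading the limits as nested make the 4-week rule pointless. The guidance for rash, hand-foot reaction, diarrhea, renal insufficiency and liver enzymes sets no recovery limit after interruption, and neither does the Grade 4 row of Table 6-2. Section 6.5.1.3 still operates there. A general outer limit with a tighter one in a single row is coherent.

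The Medical Lead sentence need not contradict the one before it. It could apply to an AE that recovered in time but where restart came later. The creatinine mismatch is likewise a difference of thresholds. With the table's criteria read as alternatives, any rise above 0.5 also exceeds 0.3. A value above 2 mg/dL from an eligible baseline below 1.5 is a rise of more than 0.5.

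What remains is that the nested reading is nowhere stated. Section 6.5.1.3 claims all related AEs, so a site could rely on it in good faith and restart where Table 6-2 requires discontinuation.

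**Conclusion.** The inconsistency is real and limited. For related Grade 2 (intolerable) or Grade 3 AEs without a specific guideline, two current mandatory passages set different limits, 3 and 4 weeks, without precedence. Outcomes differ only for recovery on days 22 to 28. The relation between the Medical Lead sentence and mandatory discontinuation is an ambiguity, not a proven contradiction.

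The documents give no frequency for recovery in that window, so the number affected is unknown. Amendment 4 reports 34 participants treated by 13-Mar-2023, out of about 40 planned. An influence on the discontinuation summaries is possible but not shown. A reader might also infer bias in the primary endpoint, but nothing here demonstrates an effect on ORR.

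The current SAP entry is dated 15-Oct-2024, before final database lock, and Protocol Section 9.2 ends the study no later than 17 months after LPFV. The LPFV date is not given. These facts suggest, without establishing, that few participants may remain on treatment.

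**What to change.** The sponsor's clinical team should:

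1. Reconcile the Grade 2 (intolerable) or Grade 3 row of Table 6-2 with Section 6.5.1.3, by a single limit or a stated precedence. This review does not propose which.
2. State how restart after 4 weeks with Medical Lead approval relates to mandatory discontinuation.
3. As a separate minor correction, reconcile the Section 6.5.2.7 text with Table 6-11 and correct the reference to Section 6.2.

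If any participant is still on treatment, this needs a written amendment under Section 14.1, with sponsor, IRB/IEC and, where required, health authority approval, plus notice to sites. It changes dosing practice only for those participants.

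If none remain, the clinical study report should note that the protocol held two limits. An optional listing could show related-AE interruptions longer than 21 days together with discontinuations for AEs. Both are needed because SAP Section 2.4.1 takes interruptions and permanent discontinuations from separate CRF fields. The dosing data are already planned for listing, so the cost is small.

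Timing of AE recovery should be limited to Grade 3 events. Protocol Section 10.1.1 requires a new entry on improvement only for Grades 3 and 4, and the AE items it describes include no field for intolerability. Even for Grade 3, an event that passes through Grade 2 may have no recorded date of reaching Grade 1, and the listing should say so.
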